4.9. Data Analyses

All analyses will be first performed separately in each of the study countries. In addition, for the primary study objectives, aggregated analyses with data from all three countries will be performed.

Baseline analyses will be conducted to characterise linaclotide users, and socio-demographic and clinical variables will be described for all users and for those subgroups of patients who were not sufficiently documented in the clinical development programme. The number and percentage of patients using linaclotide off-label will be also described.

Further, linaclotide treatment patterns will be described from index date to end of study period for linaclotide utilisation. Kaplan-Meier estimates will be used to describe time to discontinuation in the prescription or dispensation of linaclotide; and to describe switching from linaclotide to another drug used in IBS-C (laxatives, antispasmodics, prokinetics, or antidepressants). To better assess differences in time to event by the alleged reason for linaclotide prescription (IBS-C or other condition), Cox regression analysis will be employed if the proportional hazards assumption holds; if not, more complex models will be proposed, including predictor variable interactions with time.

Statistical analyses will be conducted using SAS® statistical software.

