8. RESEARCH QUESTIONS AND OBJECTIVES

8.1. Research Questions

This study will address the following primary research questions:

- What are the characteristics of patients prescribed linaclotide?
- What is the extent of linaclotide off-label use with regards to its indication?

A secondary research question will be:

- What are the linaclotide prescription patterns?

All research questions will be assessed in three different countries: the UK, Spain, and Sweden.

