8.2. Operational Objectives

- To describe the characteristics of patients prescribed linaclotide at time of first prescription (defined as socio-demographics, comorbidities (up to 15), co-medications (up to 15), and other potential variables of interest (up to 10))
- To also describe characteristics of patients by specific subgroups of interest (e.g., paediatric population, elderly population patients with diabetes, hypertension, or cardiovascular disease diagnostic codes, patients with codes for constipation only)
- To estimate the number and percentage of patients with the potential for linaclotide off-label use in the following groups: off-label/abuse/excessive use as a laxative due to the pharmacology of linaclotide within patients with eating disorders; off-label use in other types of constipation disorders distinct from IBS-C, particularly in the elderly population; and potential for off-label use in the paediatric population for chronic constipation.
- To describe the proportion and characteristics of patients prescribed linaclotide (overall and by alleged indication) who experience any of the following:
 - o Discontinuation of linaclotide (permanently during the observation period)
 - o Switching from linaclotide to drugs potentially also used by patients with IBS-C moderate to severe: laxatives, antispasmodics, prokinetics, or antidepressants (Hugin, 2003)
- To describe the duration of linaclotide treatment until discontinuation or switching

- To describe the effect of the indication (IBS-C diagnosis versus other) on the time from initiation of linaclotide to discontinuation or switching

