9.3.4. IBS Diagnosis and Severity Definition

The target indication of linaclotide is the treatment of moderate to severe IBS-C in adults. There are several Read, ICD-9 or ICD-10 codes related to IBS, but none are specific to IBS-C. In order to identify potential cases of IBS-C patients using codes, a combination of an IBS code with a code for constipation will be used. Table 4, Table 5 and Table 6 in Annex 3 include a broad list of Read codes, ICD-10 and ICD-9 codes for the identification of patients with IBS with different level of specificity, and codes for constipation to be used in combination.

There are no Read, ICD-9, or ICD-10 codes to indicate the severity of IBS. The most studied and most commonly used tools for measuring IBS severity involve quality-of-life and patient-reported symptom metrics that are not routinely recorded in the computerised databases selected for this study. Some components like symptoms or number of healthcare visits (part of the Functional Bowel Disorder Severity Index [Drossman et al., 2011]) have been previously used in the development of an IBS severity measure. However, it is not envisaged that this will be done as part of this study.

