4763.00	Faeces: mucous present	Unfrequently used
19EH.00	Mucus in faeces	Unfrequently used
198..00	Nausea	Second choice as code in IBS
1982.00	Nausea present	Unfrequently used
198..12	Nausea symptoms	Third choice as code in IBS
198..11	C/O - nausea	Unfrequently used
198Z.00	Nausea NOS	Unfrequently used
R070000	[D] Nausea	Unfrequently used
R070.00	[D] Nausea and vomiting	Unfrequently used
R093000	[D] Abdominal swelling	Unfrequently used
J16y411	Flatulent dyspepsia	Unfrequently used
19D..12	Anal symptoms	Unfrequently used
19D..11	Tenesmus symptom	Unfrequently used
19D..00	Tenesmus	Unfrequently used
19D2.00	Tenesmus present	Unfrequently used
19DZ.00	Tenesmus NOS	Unfrequently used
19E..11	Faeces symptom	Unfrequently used
19E..12	Motions – symptom	Unfrequently used
19E..00	Faeces/motions – symptoms	Unfrequently used
19F..	Diarrhoea symptoms	
19G..00	Diarrhoea and vomiting	
J525.00	Functional diarrhoea	
J43z.	Chronic diarrhoea	
J4z..	Non-infectious diarrhoea	

Abbreviations: IBS=irritable bowel syndrome; IBS-C=IBS predominately with constipation; NOS=unspecified

Patients with IBS will be identified through the following criteria:

- One or more IBS- related codes among the following: J521.00, J521.11, J521.13, Eu45324, 14CF.00.
- Alternatively, a combination of a code of abdominal pain or discomfort (in gray background and regular font) and at least two codes among those reported as “second choice as code in IBS”, “third choice as code in IBS” or “unfrequently used” (in *italics* and gray background).

Patients with only 14CF.00 will identify as prevalent IBS-C patients since the diagnosis date is uncertain.

Patients with IBS-C will be identified through the following criteria:

- Patient with IBS as specified above and one preferred code including the term “constipation”

Patients with IBS and a code for diarrhoea will be IBS-D. Patients with IBS only or meeting both criteria will be IBS-M.

Table 5. ICD-10 Codes for the Identification of IBS and Constipation

ICD-10 Code	Description	Comments
K58	Irritable bowel syndrome (IBS), irritable colon	Preferred code, check for constipation
K58.0	IBS with diarrhoea	To be used as exclusion criteria
K58.9	IBS without diarrhoea; IBS NOS	Preferred code, check for constipation
K59.9	Functional intestinal disorder, unspecified	Not specific
K59.0*	Constipation	To be used in combination with K58, K58.9, and K59.9 to identify IBS predominantly with constipation (IBS-C)

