Abbreviations: IBS=irritable bowel syndrome; IBS-C=IBS predominately with constipation ; NOS=unspecified

Patients with IBS will be identified through the following criteria:

- At least one code K58, K58.9 or K59.9 without code K58.0

Patients with IBS-C will be identified through the following criteria:

- Patient with IBS as specified above and code K.59.0

Patients with IBS-D will be identified through the following criteria:

- Patient with code K58.0

Patients with IBS-M will be all others with IBS but no criteria of IBS-C or IBS-D

Table 6. ICD-9 Codes for the Identification of IBS and Constipation

ICD-9 Code	Description	Comments
564.1	Irritable bowel syndrome (IBS); irritable colon; spastic colon	Preferred code, check for constipation
564.0, 564.00, 564.01, 564.09	Constipation	To be used in combination with 564.1 to identify IBS predominantly with constipation (IBS-C)
787.91	Diarrhoea	To be used in combination with 564.1 to identify IBS predominantly with constipation (IBS-D)

Abbreviations: IBS=irritable bowel syndrome; IBS-C=IBS predominately with constipation; IBS-D=IBS predominantly with diarrhoea

Patients with IBS-M will be identified through the following criteria:

- Code 564.1 without codes for constipation or codes for diarrhoea.

B. Database Feasibility Assessment

This section includes a summary of the databases assessed for use in the linaclotide studies, planned to be implemented in the UK, Spain, and Sweden. The feasibility assessment in Italy as a candidate country is also reported, although the coverage of the data sources investigated was not large enough to accrue sufficient sample size for this study. All databases identified were explored for feasibility and data content, as well as interest and availability in conducting the studies. This section contains the information provided by the candidate data sources contacted for this purpose.

Database Identification

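### Annex 3.A departs from the protocol's own IBS-C rule in different ways by coding system, so the on-label/off-label split would partly reflect the code lists

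*Protocol*

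**What the plan says.** Off-label use is a primary question in protocol section 8.1: "What is the extent of linaclotide off-label use with regards to its indication". Section 8.2 names, among the off-label groups, "off-label use in other types of constipation disorders distinct from IBS-C", and section 9.7.1 reports chronic-constipation patients who are not IBS-C as a subgroup. Section 9.7.2 makes IBS-C versus other conditions the Cox contrast for discontinuation and switching.

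For the definition, section 9.3.4 says that "a combination of an IBS code with a code for constipation will be used" and refers to Annex 3.A for the lists. The annex then sets these rules:

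- **ICD-10 (Table 5; Sweden and Spanish GP diagnoses).** IBS is "At least one code K58, K58.9 or K59.9 without code K58.0". Constipation (K59.0) is "To be used in combination with K58, K58.9, and K59.9 to identify IBS predominantly with constipation (IBS-C"). The same table describes K59.9 as an unspecified functional intestinal disorder and comments that it is not specific.
- **Read (Table 4; UK).** IBS is one of five listed codes or, "Alternatively, a combination of a code of abdominal pain or discomfort", with at least two further symptom codes. IBS-C adds one constipation code of the preferred class; only 19C..11 and 19C..00 carry that label. A patient with only the history code 14CF.00 is called prevalent IBS-C. For mixed IBS, "Patients with IBS only or meeting both criteria will be IBS-M".
- **ICD-9 (Table 6; Spanish hospital admissions).** 564.1 is always required. Adding 564.0x gives IBS-C and adding 787.91 gives IBS-D. IBS-M is 564.1 with neither.

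On pooling, section 4.9 says that "for the primary study objectives, aggregated analyses with data from all three countries will be performed". Section 9.7 and the comment in the ENCePP checklist mention only separate country analyses.

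**The concern.** The main text states one rule; the annex applies several, and they do not err in the same way. Where no IBS code is needed, a user with constipation but no IBS diagnosis can leave the named off-label group and count as on-label. Where only two constipation codes qualify, a coded IBS patient with constipation can lose the on-label class. Mixed patterns are sorted by whichever system the record happens to use, and Spain uses two.

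At stake are the off-label percentage in each country, comparisons between countries, any pooled figure, and the Cox contrast, all of which depend on this one classification.

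**Working it through.** **Step 1: the same patient under each rule.** The first column of results applies section 9.3.4 as worded; the others apply Annex 3.A as worded.

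| Record | Section 9.3.4 | Read | ICD-10 | ICD-9 |
|---|---|---|---|---|
| A. Unspecified functional bowel code plus constipation, no IBS code | not IBS-C | no such route | IBS-C (K59.9 + K59.0) | not IBS-C |
| B. Pain code, two further symptom codes, 19C..00, no IBS code | not IBS-C | IBS-C | no such route | no such route |
| C. History-of-IBS code only, no constipation code | not IBS-C | IBS-C by one sentence, IBS-M by another | no such code listed | no such code listed |
| D. IBS code plus a non-preferred constipation code (e.g. J520.00) | IBS-C | not IBS-C if read literally | IBS-C (K58.9 + K59.0) | IBS-C (564.1 + 564.0x) |
| E. IBS code with constipation and diarrhoea | not addressed | IBS-M | IBS-C, or IBS-D if K58.0 is present | meets IBS-C and IBS-D; excluded from IBS-M |

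Rows A to C can move users towards on-label. Row D moves UK users towards off-label. Row E depends on the system. Read also marks J521000 (IBS with diarrhoea) as an exclusion, and Table 5 has no diarrhoea code other than K58.0, so row E cannot be aligned with the codes now listed.

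**Step 2: how much of the study each rule covers.** Table 3 projects 2,674 (UK) + 2,407 (Spain) + 4,584 (Sweden) = 9,665, which reproduces the stated total. The shares are 27.7%, 24.9% and 47.4%, matching the stated 28%, 25% and 47%. The countries using ICD-10 make up 2,407 + 4,584 = 6,991, or 72.3%. Every country has at least one route to IBS-C without an IBS code. These are projections; section 9.5 reports actual 2016 counts below them.

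**Step 3: what can be said about size.** Let q be the true share of users who are not IBS-C, m the share of those relabelled IBS-C, and r the share of true IBS-C users who lose the label. Then

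observed off-label share = q(1 − m) + (1 − q)r.

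The documents give none of q, m or r; all values below are assumptions.

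- With r = 0 and q = 0.40: m = 0.10, 0.20, 0.30 gives 0.40 × 0.90 = 36%, 0.40 × 0.80 = 32%, 0.40 × 0.70 = 28%.
- With r = 0, q from 0.20 to 0.60 and m from 0.10 to 0.30, the shift runs from 0.20 × 0.10 = 2 points to 0.60 × 0.30 = 18 points downwards. The sampling 95% half-width at q = 0.40 is 1.96 × √(0.40 × 0.60 / 9,665) = 0.98 points.
- The shift reverses once r exceeds qm/(1 − q). At q = 0.40 that is 0.04/0.60 = 6.7%, 0.08/0.60 = 13.3% and 0.12/0.60 = 20% for m = 0.10, 0.20 and 0.30. The sign therefore depends on a quantity that the documents do not give.
- Unequal m by country, r = 0, same true 40% everywhere: m = 0.10 in the UK and 0.30 in Spain and Sweden gives 36% against 28%, an 8-point gap from the rules alone, and a pooled (2,674 × 0.36 + 6,991 × 0.28)/9,665 = 30.2%. Reversing the two gives (2,674 × 0.28 + 6,991 × 0.36)/9,665 = 33.8%.

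**Step 4: the Cox contrast.** If a share c of the IBS-C group is really other, a simple hazard-averaging approximation gives observed HR ≈ HR/[(1 − c) + c × HR]. Taking HR = 1.2, the detectable value in section 9.5, c = 0.10 gives 1.2/1.02 = 1.18 and c = 0.30 gives 1.2/1.06 = 1.13. Again c is assumed.

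**The case against.** The protocol is open about the difficulty. Section 9.3.4 says that no code is specific to IBS-C, speaks of potential cases, and describes the annex lists as broad and of varying specificity. Section 9.9 expects misclassification between IBS-C and chronic constipation. On this view the annex puts 9.3.4 into operation, and three code systems must differ somewhat. That is fair as far as it goes, but disclosure is not a remedy. K59.9 and 14CF.00 alone are choices, not necessities, since each system has an IBS diagnosis code.

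The UK symptom route has a better defence. Section 7 describes IBS as abdominal pain, bloating and altered bowel habit, and the route follows that description. Demanding a diagnosis code would push genuine but under-coded IBS-C into off-label. This is a trade-off between sensitivity and specificity, and the documents do not say which error is larger. How permissive the route is also depends on shading and italics that the available text does not fully preserve. The reasonable request is therefore to make its effect visible, not to call it an error.

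On row D, Table 4 comments that non-preferred constipation codes are combined with IBS, so the authors may have meant to count them. The rule beneath the table says otherwise, and the two need to agree.

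A separate SAP is listed in Annex 1 and may add sensitivity analyses; their absence here is not the point. The point rests on rules that the protocol itself states.

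**Conclusion.** The concern holds as an inconsistency of definition. Annex 3.A does not apply the rule in section 9.3.4, departs from it differently by coding system, contradicts itself on 14CF.00, and sorts mixed patterns in three ways. The primary off-label split and the IBS-C versus other comparison would partly reflect the code lists.

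A reader might infer that off-label use will be understated, for instance 36% to 28% against a true 40%. The documents do not support that as a net effect: the preferred-code restriction works the other way in the UK, and both the 40% and the relabelling rates are assumed. Nor can it be taken as settled that one pooled figure will be reported, since only the abstract plans aggregation. Country-level estimates are affected in either case.

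**What to change.** For the main off-label estimate, require in every system an IBS diagnosis code (Read J521.00, J521.11, J521.13, Eu45324; ICD-10 K58, K58.9; ICD-9 564.1) plus any constipation code listed for that system.

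- Move K59.9, and 14CF.00 alone, out of the main IBS-C definition into a possible-IBS-C sensitivity analysis by country. State how 14CF.00 with a constipation code is handled, and remove its conflict with the IBS-M sentence.
- Report the UK symptom-only route as a separate row so that its effect can be seen.
- State one rule for patients with both constipation and diarrhoea codes and apply it in all systems, adding ICD-10 diarrhoea codes as needed.
- Align section 9.3.4 with the annex, and reconcile section 4.9 (aggregated analyses) with section 9.7 (separate analyses).

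The cost is code-list edits, including some new codes, and one extra table. Some true but under-coded IBS-C patients leave the main IBS-C group, while the UK group may gain patients whose constipation codes are not in the preferred class.

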 - Bacterial/viral/parasite lab information, when available (positive versus negative or no information)

For prevalence of chronic comorbidities, prior diagnoses, or history of digestive surgery at index date, the patient's entire medical history will be explored.

9.3.3. *Linaclotide Treatment Outcomes*

Secondary outcomes of this study will be linaclotide treatment patterns. The linaclotide exposure information is characterised by the linaclotide days of supply. Days of supply will be ascertained from the prescription/dispensation information recorded in the databases and the recommended dose (one capsule of linaclotide 290 µg taken once per day) and calculated by dividing the quantity prescribed/dispensed by the daily dose. Days of supply of one prescription/dispensation are expected to be around 28 days since the 28-capsule pack will be the most widely used package size. If package size is unknown, then the median duration for patients with this information will be used (and if no median can be estimated then 28 days will be used).

Linaclotide prescription patterns of interest are:

- Discontinuation of linaclotide: defined as no prescription of linaclotide in the period of 1.5 times the number of days of supply of the last linaclotide prescription following its expiry date (Sikka et al., 2005; Peterson et al., 2007): for example, for a 28-day prescription, no new prescription in the 43 days after the expiry date of the prescription supply. The date of discontinuation is the day after the date of expiry of the last linaclotide prescription. Time to discontinuation (permanently during the study period or temporarily) is the interval between the date of the first linaclotide prescription and the date of discontinuation. Discontinuation

will be reported separately for those who permanently discontinue during the study period and for those who discontinue temporarily and subsequently restart on linaclotide (see below).

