9.9. Limitations of the Research Methods

Categorisation of patients with IBS into IBS-C, IBS-D, or IBS-M might be challenging. Differentiation between IBS-C and chronic constipation will also be challenging. As a consequence, some degree of misclassification is to be expected.

The use of over-the-counter medications for the treatment of IBS-C-related symptoms, constipation, and diarrhoea is acknowledged as another study limitation (Hungin, 2003). Over-the-counter medications will not be available in the UK or in Sweden. For Spain, we will include over-the-counter medications; however, we expect under-recording of these in the database.

The CPRD provides a large, diverse, and representative sample of UK people using primary care services, which allows for generalizability of the study findings to the broader UK population. The CPRD (and its predecessor General Practice Research Database [GPRD]) have been widely used for observational studies, with over 890 studies published to date in peer-reviewed journals. The SIDIAP database includes information for 90% of the population resident in Catalonia, a region in the north-east of Spain, and resembles the data collected by UK databases. One limitation is that date of prescription is available for only the first prescription and, thereafter, only approximate date of dispensation is available. For Sweden, the NPR and PDR cover the entire Swedish population and have been previously used in observational studies including drug utilisation ones. However, no primary care data will be available, so diagnoses will be those determined by a specialist, which are expected to be required for the variables of interest for this study. The PDR is not complete with regard to drugs used in nursing homes. According to the National Board of Health and Welfare, about 1% of people aged 65–79 years live in nursing homes, and about 20% of people aged 80 or more years live in nursing homes in Sweden [Socialstyrelsen]. This may be reflected in potential lower numbers of elderly patient using linaclotide identified in Sweden.

The validity of research findings based on CPRD data as well as the other databases depends on the quality and completeness of data recorded. We are only able to identify comorbidities for which the patient has consulted their GP. Referrals are not always uniformly coded and may appear as free-hand text or letters within the database.

Interval censoring might have an impact on the precision of the results.

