Some of the challenges mentioned for the safety study were that the exact date of the prescription is only available for the first prescription. For subsequent prescriptions, only the month when it was dispensed by the pharmacy will be available. Identification of complication outcomes based on codes might be incomplete due to inconsistent recording and could be difficult to relate an episode of diarrhoea to potential complications. However, these challenges could be overcome by the use of questionnaires to a sample of physicians or the use of free text in the medical records of patients.

Alternative Candidate: Instituto Aragonés de Ciencias de la Salud (IACS)

The Public Health and Health Services Research at the IACS in the Spanish region of Aragón, has the possibility to link different electronic medical and administrative databases in the region for research purposes. With data covering 126,838 patients from six urban health centres in one Health Sector of Zaragoza, IACS covers a small percentage of the Spanish population (0.27%). When linked, these different databases provide administrative and clinical information from outpatient clinics (primary care health centres), administrative and clinical information from specialty clinics, emergency room diagnoses and care, hospital procedures and discharge diagnoses, and pharmacy prescription data.

However, the IACS does not maintain any database and, currently, each of the linkable databases belongs to two different governmental organisations which collect the data, either the Servicio Aragonés de Salud or the Departamento de Sanidad Bienestar Social y Familia. To gain access to these data, it is required to apply to each of the data custodians by presenting a research protocol with the post-authorisation approval. Then an extraction of data would be performed, tailored for each particular study. Managing a study of this kind will require, the participation of one of their researchers as principal investigator, who will be responsible for the good use of the *ad hoc* database created. Information on GP-diagnosed conditions uses the International Classification of Primary Care coding and on GP prescriptions the ATC classification codes.

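### With approximate, month-level refill dates in Spain, the day-level discontinuation rule cannot be decided for refill gaps of roughly 60 to 91 days, which affects event status and not only precision

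*Protocol*

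**What the plan says.** Section 9.3.3 defines discontinuation as no linaclotide prescription "in the period of 1.5 times the number of days of supply of the last linaclotide prescription following its expiry date". Its worked example is "for a 28-day prescription, no new prescription in the 43 days after the expiry date of the prescription supply". Section 9.2.2.2 ends follow-up at 2.5 times the last supply plus one assessment day. Switching (Section 9.3.3) requires the other drug to start during linaclotide treatment and to continue past discontinuation, so it depends on the order of dates around expiry. These rules are written once for all three countries.

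On Spanish dates, Annex 3.B reports under SIDIAP: "Some of the challenges mentioned for the safety study were that the exact date of the prescription is only available for the first prescription". It continues: "For subsequent prescriptions, only the month when it was dispensed by the pharmacy will be available". Section 9.9 repeats the limit among the limitations of this study: "date of prescription is available for only the first prescription and, thereafter, only approximate date of dispensation is available". Sections 4.7 and Annex 3.B also list dates of prescription and dispensation as available in SIDIAP without mentioning any limit.

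The only consequence for time-to-event results that Section 9.9 names is "Interval censoring might have an impact on the precision of the results".

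**The concern.** Interval censoring describes an event that is known to have happened at a time known only within a range. Month-level refill dates do more than that. If the dispensing-to-dispensing gap is known only to within about a month either way, it may be unknown whether the gap passed the cut, and therefore whether a discontinuation occurred at all.

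The Spanish proportion discontinuing, the Kaplan-Meier curve for first discontinuation and the split between discontinued, switched and censored would then depend partly on the day assigned to each refill. These are secondary, descriptive outcomes. Spain was nevertheless projected at 25% of the cohort (Section 9.5), and country results will naturally be read side by side.

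**Working it through.** **Inputs.** Pack of 28 days, gap of 1.5 times supply, and the 43-day example (Section 9.3.3); one extra assessment day and study end on 31 December 2017 (Section 9.2.2.2); month-only refill dates in SIDIAP (Annex 3.B). Assumptions: the day assigned within a month, and dispensings spread evenly over calendar days.

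**1. The plan's own figure.** 1.5 × 28 = 42 days after expiry, and 42 + 1 assessment day = 43. The definition and the example agree once the extra day is counted. Measured from the last dispensing, the cut is 2.5 × 28 = 70 days, or 71 with the extra day.

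**2. What a month difference can mean.** All pairs of calendar days were enumerated.

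| Calendar months between dispensings | Possible true gap (days) | Position relative to the 70-day cut |
|---|---|---|
| 1 | 1 to 61 | always below |
| 2 | 29 to 91 | straddles |
| 3 | 60 to 122 | straddles |
| 4 | 90 or more | always above |

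With days uniform within months (2015 to 2017), 23% of two-month pairs exceed 70 days and 5% of three-month pairs do not. These are shares of date pairs, not of patients.

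**3. Misclassification at a given true gap.** With both dates set to the 15th, a two-month difference is always 59 to 62 days and a three-month difference 89 to 92 days. The rule therefore becomes: discontinued if the months differ by three or more. A true 70-day gap crosses three month boundaries for 337 of 1,148 start days from 1 September 2014, so 337/1,148 = 29% are falsely called discontinued. A true 75-day gap crosses only two for 621 of 1,143 start days, so 621/1,143 = 54% are missed.

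| True gap (days) | 65 | 70 | 71 | 75 | 80 | 84 | 90 |
|---|---|---|---|---|---|---|---|
| Misclassified (70-day cut) | 13% | 29% | 67% | 54% | 38% | 25% | 5% |

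Errors are false discontinuations up to the cut and missed ones above it. The unweighted mean over gaps of 60 to 91 days is 27% (26% with the 71-day cut). First-of-month assignment gives the same figures. If the index date is exact and the first refill is set to mid-month, the affected window is 57 to 86 days and the error peaks at about 50%.

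**4. Switching.** Set the linaclotide dispensing to mid-month and keep the other drug's date exact (assumption). A start 7 days before, on, or 7 days after the true expiry is then put on the wrong side of expiry 28%, 51% and 26% of the time.

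**5. Study end.** The last dispensing date with a full window is 31 December 2017 minus 70 or 71 days, that is 22 or 21 October 2017. An October 2017 dispensing known only by month cannot be sorted into discontinued or censored.

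**6. Who is unaffected.** Refills every 28 days differ by at most one calendar month and are never called discontinued. A patient who never refills remains a discontinuer, with an imprecise date, unless the last dispensing falls near study end.

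**The case against.** Several points on the other side have force.

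- The limitation is disclosed. The interval-censoring sentence in Section 9.9 stands alone and does not name Spain, and the same section says in general terms that validity depends on data quality. This stands in part: the protocol does not say outright that Spanish dating costs precision alone, but nowhere does it say that event status is at risk.
- A day-assignment rule may sit in the SAP, which is not at hand, and its absence here is no finding. That stands. However, such a rule only selects a classification and cannot recover the missing days.
- Annex 3.B raises month-only dates for the safety study, suggests remedies such as physician questionnaires, and reports that the SIDIAP team was confident about the utilisation study. Section 9.9 nevertheless applies the limit to this study, although it says approximate rather than month-only.

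Stronger readings are tempting but not supported:

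- A reader might infer that Spanish events in general are misclassified. Only gaps near the cut are affected, and Section 9.5 expects about one-third of patients to stop after one pack, for whom status is clear away from study end.
- A reader might infer that the intermittent third of users sits on the boundary, since 28 × 365/150 = 68 days. That holds only if single packs are evenly spaced. One continuous 150-day course fits the same assumption and produces no such gaps.
- A reader might infer biased hazard ratios. Nothing shows that the rounding differs by indication, and no bias can be computed.
- A reader might infer that a planned country comparison fails. Section 9.7 analyses countries separately, Section 4.9 confines aggregated analyses to the primary objectives, and the UK uses prescriptions rather than dispensings in any case.

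**Conclusion.** The point holds within limits. If Spanish refill dates are known only to the month, the protocol's rule cannot be decided for true gaps of about 60 to 91 days. At 70 and 75 days the error is about 29% and 54% under mid-month assignment, and it runs in both directions. Switching order around expiry, and status after dispensings around October 2017, are uncertain for the same reason.

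These rates are conditional on the gap and on the assumed day assignment. The protocol gives no distribution of refill gaps, so neither the share of Spanish patients affected nor the net effect on any estimate can be stated. Because the outcomes are secondary and descriptive, this should be corrected but does not threaten the primary objectives.

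**What to change.** - **Spain:** state the discontinuation and switching rules in calendar months (for example, no dispensing in a fixed number of whole months after the month of expiry). Analyse on that scale with life-table estimates and a complementary log-log model for grouped times, which still yields hazard ratios.
- **Sensitivity analysis:** re-run Sweden, which has exact dispensing dates, and the UK with dates rounded to the month under the same rule. Comparing these with the exact-date results measures the misclassification, and gives a like-for-like version for any side-by-side reading of countries. Note that the UK still counts prescriptions.
- **Section 9.9:** say that approximate Spanish dates can misclassify event status and event date for gaps near the cut, as well as reduce precision. Reconcile the unqualified SIDIAP date descriptions in Section 4.7 and Annex 3.B with this limit.

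No new data are needed. The cost is coarser Spanish time estimates, which the data already impose, and a small amount of extra programming.
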